Analyses are conducted at the individual employee level and at the worksite level. The treatment period in our phase 2 analysis is defined as the 36-month period spanning January 2015 through December 2017. (In comparison, the phase 1 analysis spanned January 2015 through mid-2016).

A. Intention-to-treat analysis

In the individual-level intention-to-treat (ITT) analysis, our goal is to estimate the average effect of a worker being randomized into a treatment worksite on outcomes of interest. Given that the

⁹ Zubizarreta JR. Stable weights that balance covariates for estimation with incomplete outcome data. *Journal of the American Statistical Association*. 2015 Sep;110(511):910-922; Wang X, Zubizarreta JR. Minimal approximately balancing weights: Asymptotic properties and practical considerations. *Biometrika*. 2017;103(1):1-22; Hirshberg DA, Zubizarreta JR. On two approaches to weighting in causal inference. *Epidemiology*. 2017;28(6):812-816.

treatment is implemented at the worksite level and that there are likely fixed costs of the program, the ITT estimates (and the worksite level analysis) are informative.

We use a base specification that includes a dose-response measure of the effect of exposure to the intervention (as measured by time worked). This specification captures the overall effect of randomization into treatment as well as how the effect of randomization to a treatment site varies with additional exposure to the treatment.

$$Y_{ijt} = \beta_0 + \beta_1 TREATMENT_{jt} + \beta_2 TIME_WORKED_{ijt} + \beta_3 TREATMENT_{jt} * TIME_WORKED_{ijt} + \beta_4 X_{ijt} + \varepsilon_{ijt} \quad (1)$$

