In this representative estimating equation, Y_{ijt} denotes an outcome of interest, such as medical spending, for individual i who is employed in worksite j at time t . $TREATMENT_{jt}$ is a binary indicator of whether the individual's worksite was randomized into treatment or control. We assigned each individual to the worksite at which he or she was employed when the treatment began in January 2015. $TIME_WORKED_{ijt}$ is the share of total available work hours in the study period that the individual actually worked; it is expressed in percentage terms. The effect of randomization to a treatment worksite is allowed to vary based on exposure to the treatment (measured via time worked during the treatment period). The treatment effect is captured by $\beta_1 + \beta_3 * Exposure$. The average effect of randomization into the treatment group can be summarized by assessing this at the average level of exposure. While we will produce estimates of the average effect of randomization into treatment, as captured in the layout of Tables 3-6, we will additionally show results for both β_1 and β_3 for each of our results in a set of parallel tables.

X_{ijt} represents a vector of covariates that may help improve precision as well as account for chance differences in characteristics between treatment and control groups, including:

- Age indicators: <20 years (omitted), 20-29, 30-39, 40-49, 50-59, and 60 and greater.
- Sex indicator: male (omitted), female
- Age-sex interactions
- Race: white (omitted), black, Hispanic, and other
- Employment characteristics (measured at baseline for the stably employed subsample):
 - Part-time (omitted), full-time
 - Salaried (omitted), hourly
 - Sales worker (omitted), non-sales worker, and other worker.

ε_{ijt} is the idiosyncratic error term. The models are weighted using the sample weights described above. Standard errors were clustered at the worksite level.

B. Local average treatment effect (LATE)

While our ITT analysis explores the effect of being randomized into a treatment worksite, a related but distinct question is: what is the effect of participating in the wellness program on the outcomes of interest? The answer to this second question will be different if not all employees in treatment worksites elect to participate. Because the choice to participate in the program is endogenous, simply including participation as a right-hand side variable may produce biased

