randomization into treatment or control, with β_1 indicating the average worksite-level effect of being randomized into treatment. The vector of covariates X_{kt} comprises the same set of observable characteristics for individuals, aggregated to the worksite level using weighted averages (generating percentages for binary variables). The worksite-level regressions are weighted by worksite size, as measured by the total hours worked by all employees at a worksite, with standard errors adjusted for heteroscedasticity. For estimates of program effect that are significant in the individual-level analysis, we will produce parallel LATE estimates at the workplace level, analogously using treatment status as an instrument for participation.

Although the employees at each worksite could change over time, the worksites themselves were all stably represented in our data. However, at the 18-month mark, 5 worksites previously in the control group entered the treatment group. In our base specification, we will assess effects for the 20 worksites that were continuously treated throughout the 3-year period (omitting the additional 5 from the analysis altogether). As an alternative specification, we will also evaluate effects at the worksite level when considering the 5 additional worksites in the treatment group.

F. Sensitivity analyses

We conduct several types of sensitivity analyses. First, in the statistical analyses above, our base regression models use linear regression even for binary outcomes. The OLS estimator has been shown to perform better than other non-linear approaches in estimating the average population effect, particularly with large samples.¹⁰ However, OLS also has limitations, such as its sensitivity to outliers. To test the robustness of our main results to changes in functional form, we will fit logit models for binary outcome variables.

Second, we will present LATE results with alternative definitions of participation. As defined above, these include a binary indicator of participation based on completing at least one module, and a high participation indicator defined as completing at least 3 modules.

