Additionally, our phase 1 analysis of the first 18 months used a different baseline specification that did not allow for treatment effects to vary with individuals' exposure (rather, weighting individuals by exposure). It also included a different sample, as 5 additional worksites from the previous secondary control group were added to the treatment group and another 5 to the primary control group at the 18-month mark. Therefore, to facilitate comparisons of results between this phase 2 analysis to those from phase 1, we will present results using the phase 1 statistical model and set of weights on the phase 2 sample, as well as results using the phase 2 model and weights on the phase 1 sample.

Specifically, we conduct the ITT and LATE analyses using the phase 1 specifications that include just a treatment dummy. The ITT specification is:

$$Y_{ijt} = \beta_0 + \beta_1 TREATMENT_{jt} + \beta_2 X_{ijt} + \varepsilon_{ijt} \quad (7)$$

¹⁰ See, for example, Buntin and Zaslavsky, 2004; Manning, Basu, and Mullahy, 2005; Ellis and McGuire 2006; Jiang, Ellis, and Kuo, 2008.

The LATE specification is:

[figure not shown]
$$Y_{ijt} = \gamma_0 + \gamma_1 PARTICIPATION_{ijt} + \gamma_2 \mathbf{X}_{ijt} + \mu_{ijt} \quad (8)$$

With first stage regression:

$$PARTICIPATION_{ijt} = \pi_0 + \pi_1 TREATMENT_{jt} + \pi_2 \mathbf{X}_{ijt} + v_{ijt} \quad (9)$$

[figure not shown]
We conduct this analysis first for our full sample, and then for the subsample of treatment and control sites that match the phase 1 sample.

Figure 1: Locations of Treatment and Primary Control Worksites, Phase 2

Notes: This map shows the 25 treatment and 25 control worksites in Phase 2 of the treatment. Red markers designate treatment worksites; red triangles are the 5 additional treatment worksites that were added in Phase 2. Blue markers designate primary control worksites; blue triangles are the 5 additional primary control worksites that were added in Phase 2.

Figure 2. CONSORT Flow Diagram

Average number of employees per club = 304 (SD =88)
 Employees insured through Cigna during June 2016 (the midpoint of the study period) = 6,686 (37.34%)
 *Surveyed employees as a percent of all employees who worked between 8/1/2017 and 10/30/2017

Notes: This CONSORT diagram shows the flow of the trial and sample sizes through phase 2.

Table 1: Timeline of the Workplace Wellness Program

	Phase 1												Phase 2																							

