Notes: Table reports the coefficient on TREATMENT from estimating equation (1) by OLS (column 2), and the coefficient on PARTICIPATION from estimating equation (2) by IV (column 3). Standard errors are listed in parentheses. Column 1 reports the mean of each employment outcome in the control group for each sample (with standard deviation in parentheses, followed by the number of observations for each outcome). All regressions will include demographic and employment controls (age, sex, age-sex interactions, race/ethnicity, Cigna coverage status, full-time status, paid hourly status, and job category) and cluster standard errors at the worksite (for employee-level regressions). Employee-level and stably employed subsample control means are weighted by a weight that balances treatment and control on demographic characteristics. Worksite-level control means are not traditionally weighted: individual-level records are collapsed at the worksite-level and weighted by the total number of hours worked at each worksite. For worksite level results on tenure, the outcome was defined as the percent of total days at the worksite during the study period that was worked by employees at the worksite.

§ Tenure was defined as the number of days worked during the treatment period for the employee-level mean and stably employed subsample mean; it was defined as the percent of the entire treatment period worked by employees in the worksite-level mean.

Table 4: Impact on Medical & Pharmaceutical Spending and Utilization

	Employee-level			Stably Employed Subsample			Worksite-level (per 2000 work hours)		
	Mean in Control Group (1)	Reduced Form (Linear) (2)	2SLS (Linear) (3)	Mean in Control Group (1)	Reduced Form (Linear) (2)	2SLS (Linear) (3)	Mean in Control Group (1)	Reduced Form (Linear) (2)	2SLS (Linear) (3)
Medical Spending									
Total Spending	4800.57 (18559.82)			4721.85 (19056.92)			5044.74 (2994.54)		
Medical Utilization									
Number of Office visits	3.90 (4.47)			3.95 (4.33)			4.21 (0.93)		
Number of Hospitalizations	0.09 (0.40)			0.08 (0.36)			0.08 (0.05)		
Number of ER Visits	0.28 (0.75)			0.26 (0.61)			0.27 (0.11)		
Pharmaceutical Spending									
Total Spending	1237.60 (6921.32)			1227.32 (7115.67)			1317.72 (1145.17)		
Pharmaceutical Utilization									
Number of Distinct Medications	5.49 (6.44)			5.91 (6.54)			6.00 (1.30)		
Total Medication Months	11.20 (19.31)			11.41 (19.37)			12.39 (4.38)		
N	7,174			5,779			135		

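### The notes to Tables 3–6 put the effect at zero time worked in the employee-level and stably employed columns, where section VI.A promises the average effect

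*Combined protocol and SAP*

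**What the plan says.** Section VI.A (Intention-to-treat analysis) gives the employee-level base model. Equation (1) contains TREATMENT, TIME_WORKED and their product, plus covariates. TIME_WORKED "is the share of total available work hours in the study period that the individual actually worked; it is expressed in percentage terms". The section does not say that it is centred.

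The same section defines the treatment effect as β1 + β3 × Exposure and adds: "The average effect of randomization into the treatment group can be summarized by assessing this at the average level of exposure". It then allocates the results to tables: "While we will produce estimates of the average effect of randomization into treatment, as captured in the layout of Tables 3-6". β1 and β3 are to be shown as well, for every result, "in a set of parallel tables".

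The notes under Tables 3, 4, 5 and 6 all open with the same description of column 2: "Table reports the coefficient on TREATMENT from estimating equation (1) by OLS (column 2". For column 3 they cite an equation (2).

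Two other models bear on the point:
- The worksite model in VI.E, equation (6), has no exposure term. Its TREATMENT coefficient is described as "indicating the average worksite-level effect of being randomized into treatment".
- VI.F adds, for comparison with the earlier results, the "phase 1 specifications that include just a treatment dummy" (equation 7).

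**The concern.** In a model with an interaction, the coefficient on TREATMENT alone is the treatment effect where the interacting variable is zero. Here that is an employee who worked none of the available hours and so had no opportunity for exposure. The notes therefore name a different quantity from the one VI.A assigns to the same column.

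The affected columns are the main results for employment, spending and utilization, biometrics and self-reported health. A programmer working from the notes would fill them with β1. If the program acts through exposure, β1 could be near zero while the average effect is not, and it would also be estimated less precisely. The plan's stated purpose is to limit specification searching, yet as written it supports two different numbers for one column.

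**Working it through.** The estimate columns of Tables 3–6 are blank in the plan, so there is no stated figure to reproduce. The check is algebra plus a rough size.

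**1. What each text reports.** From equation (1), the effect of TREATMENT at time worked *x* is β1 + β3*x*.
- Table notes: the coefficient on TREATMENT, that is *x* = 0, giving β1.
- VI.A: *x* = mean exposure, giving β1 + β3 × mean.
- Difference: β3 × mean. It vanishes only if β3 = 0 or if TIME_WORKED is centred. The plan states neither.

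**2. Range of the difference**, as a share of the average effect, (β3 × mean)/(β1 + β3 × mean):
- effect that does not vary with exposure (β3 = 0): 0%;
- effect proportional to exposure (β1 = 0): 100%.

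**3. How far zero is from typical exposure.** The plan gives no mean of TIME_WORKED. As an assumed stand-in, take control-group tenure in days from Table 3, over the 36 months from January 2015 through December 2017 (365 + 366 + 365 = 1,096 days).

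| Sample | Mean (SD) days | Mean share | SD share |
|---|---|---|---|
| All employees | 416.69 (399.87) | 416.69/1,096 = 38.0% | 399.87/1,096 = 36.5% |
| Stably employed | 786.57 (376.96) | 786.57/1,096 = 71.8% | 376.96/1,096 = 34.4% |

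**4. Precision.** Suppose exposure has the same mean and SD in both arms, and ignore clustering, weights and covariates. The variance of the estimated effect at *x* is then proportional to 1 + (*x* − mean)²/SD². Hence SE(β1)/SE(average effect) = √(1 + mean²/SD²).
- All employees: √(1 + (416.69/399.87)²) = 1.44.
- Stably employed: √(1 + (786.57/376.96)²) = 2.31.

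**5. Check of the algebra by simulation.** The effect was set at 0 for no exposure and 1.0 for full exposure, using the plan's sample sizes. The mean estimates of β1 were −0.004 (all) and 0.03 (stably employed). The effect at mean exposure was 0.38 and 0.72. The simulated SE ratios were 1.47 and 2.21. Centring TIME_WORKED made the TREATMENT coefficient equal to the effect at mean exposure. The zero for β1 follows from the assumed effect, so this confirms the formulas and says nothing about the trial's own effect.

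**6. Other columns and tables.**
- Worksite columns of Tables 3 and 4: under equation (6) the TREATMENT coefficient is already the average effect. The note only cites the wrong equation.
- Equation (2) does not appear in the text; the numbering runs (1), (3), (4). The participation model is equation (3).
- Table 10, Panel A, all employees: the first-stage values lie close to simple differences between the treatment means in Table 7, Panel B and the control means in Table 10. These are 27.53 against 28.4 − 0.21 = 28.19 (any module, %), 1.12 against 1.17 − 0.01 = 1.16 (modules), and 15.95 against 16.7 − 0.12 = 16.58 (three or more, %). They look like average effects, not effects at zero exposure.

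**The case against.** The strongest reply is that VI.A already settles the matter: it defines the average effect, places it in Tables 3–6, and sends the separate coefficients elsewhere. On this view the fault is a caption left over from a treatment-only model, and the reference to a missing equation (2) points the same way. That origin is an inference, but the intent of VI.A is clear. This stands, and it makes the point a conflict between text and table notes, not a missing or wrong estimand.

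The plan also limits the harm. β1 and β3 are to be reported for every result, so an effect that grows with exposure would show in β3. Equation (7) is planned on the phase 2 sample, and equation (6) covers administrative outcomes at worksite level. A reader might infer that a null headline table would hide a real effect; with these analyses reported alongside, the documents do not support that as the likely outcome.

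Two further inferences go too far. One is that Table 10 has the same fault. Its note speaks of first-stage estimates of the impact of TREATMENT and never names the zero-exposure coefficient of equation (4). The other is that the 100% loss measures this trial; it is one end of a range, fixed by assumption.

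Finally, evaluating equation (1) at mean exposure is not a clean intention-to-treat effect. Time worked is measured after randomization, and VI.C counts tenure and time worked among the primary outcomes. The contrast equals the average effect of assignment only if treatment leaves time worked unchanged. This stands and shapes the fix for the tenure row.

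None of this removes the conflict: the notes and VI.A still name different quantities for the same column.

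**Conclusion.** The point holds for the employee-level columns of Tables 3–6, in the full and the stably employed samples. As written, the notes call for the effect at zero time worked, while VI.A calls for the effect at average exposure. The two differ whenever β3 is not zero, by 0% to 100% of the average effect between a constant effect and one proportional to exposure.

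The SE ratios of about 1.4 and 2.3 rest on control days worked as a proxy for share of hours, and they ignore clustering and weights. They come from the Table 3 samples. No exposure figure is given for the Cigna sample (Table 4) or for the screening and survey completers (Tables 5 and 6). The conflict itself depends on none of these assumptions.

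The worksite columns are unaffected apart from the equation cited, and no error in the values of Table 10 is shown. The point should be settled before the estimate columns are filled, because it decides which number goes into the headline column.

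**What to change.** - **Column 2, employee-level and stably employed.** Change the notes to β1 + β3 × mean TIME_WORKED, with the clustered standard error of that linear combination. Centring TIME_WORKED at the same mean before forming the product gives the same estimate. State which mean is used (which sample, and whether weighted). Keep the zero-exposure β1 and β3 in the parallel tables.
- **Worksite columns of Tables 3 and 4.** Cite equation (6).
- **Column 3.** Replace the reference to equation (2) with equation (3).
- **Tenure row of Table 3.** TIME_WORKED is close to the outcome itself, so conditioning on it gives no meaningful average effect. Report the treatment-only model, equation (7). State the weights: VI.F says the phase 1 analysis weighted individuals by exposure, and those weights would bring time worked back in.
- **Table 10.** Add a label naming the model and the quantity shown: equation (9), or equation (4) evaluated at mean exposure.

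The cost is rewording the notes and a line of code per model. No new data are needed.

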- **Hours and earnings:** Each employee's hours (including working hours, vacation, sick time, personal time) and earnings in each pay period. Each observation is at the employee, pay-period, earnings-type level. These data include a handful of negative payments/hours that indicate corrections.

We used these data to study several outcomes:

- **Absenteeism:** We calculated absenteeism as an employee's number of sick plus personal hours, divided by the sum of an employee's number of sick, personal, and worked hours. This gives the ratio of absence relative to how much an employee usually works. Vacation and holiday time are excluded from both the numerator and denominator.
- **Performance review:** Employee performance reviews were coded on a 5-point scale, with 1 representing the best performance rating and 5 the worst. We averaged performance review scores (weighted by the duration of time over which a score held) and created a binary indicator where a score of less than 3 was coded as good performance and 3 and greater as poor performance.
- **Employment tenure:** We calculated each worker's length of tenure at BJ's and how many hours he or she worked (including the nature of those hours, such as regular hours and overtime). We defined tenure as the difference between the hire date and the latest

termination date. If there was no hire date recorded in the data, we used the first appearance in our database. If there was no termination or retirement date in the data, we used the end of the study period.

Table 2 provides a summary of demographic and employment characteristics of the population. The data are presented at the employee level (overall and for analytical subsets) and at the worksite level. **Table 3** provides summary statistics for tenure, performance review, and absenteeism gathered among the control worksites during the treatment period.

A2. Medical and pharmaceutical claims data

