The key identifying assumption is that the only mechanism through which being employed in a treatment worksite affects outcomes is through the availability of the wellness program. There are two threats to this assumption. First, to the extent that covariates were not balanced at baseline and those covariates affect the outcomes of interest, that imbalance could bias our estimates. We control for observed covariates and apply weights to balance covariates between treatment and control. Despite these adjustments, unobserved covariates might still be imbalanced.

Second, to the extent that the wellness program affected hiring or tenure of employees, their presence in the data set may be endogenously determined. We address the issue of endogenous entry by pre-specifying a subsample of those who were already employed at the time the intervention began. We defined this more restrictive “stable employment” subsample as comprising employees who had worked continuously for 13 weeks prior to the wellness program. This comes at a cost of reducing the overall sample size. Our goal in choosing the definition for this subsample was to balance the costs and benefits, as detailed in Appendix 2.

In this stably employed subsample, however, exit from the firm's workforce is still potentially endogenous. We deal with this concern in two ways. First, we will test balance on exit between treatment worksites vs. from control worksites overall and for subgroups. Indeed, tenure and time worked are among our primary outcomes. To the extent that we observe any unbalanced exit, we will perform a bounding exercise (assuming that those who exited have outcomes working against any observed effects of the intervention).

D. Subgroup analyses

We pre-specified three subgroup analyses. We selected these subgroups based on differences in key outcomes within the control group for those with different baseline characteristics, such as differences in medical spending by age or in reported exercise by sex (**Table 11**).

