Appendix 2. Determination of the Stably Employed Subsample

[figure not shown]
We conducted an analysis of the duration of employment (tenure), which informed our definition of the pre-specified stably employed subsample. This analysis of tenure is described below.

Figure 1A looks at a number of scenarios where we take samples of treatment (T) and control (C) workers who were employed for varying numbers of consecutive weeks starting on 1/1/2014. In each scenario, we follow the samples of workers until they reach 1/1/2015 and look at how many of them are still employed. To be precise, for each restriction criterion of the number of consecutive weeks worked starting 1/1/2014 (X axis), the height of the dark blue bar (C 14) depicts the total number of control workers in the sample and the height of the light blue bar (C 15) depicts the total number of control workers who were still working on 1/1/2015. Analogously, the height of the black bar (T 14) represents treatment workers who started in the sample on 1/1/2014 and the height of the gray bar (T 15) represents treatment workers who were still working on 1/1/2015. Of note, the bars are overlapping for each X (i.e. they are not stacked; rather they all originate at 0). The solid and dotted lines merely reflect the percentages of C and T employees, respectively, who were still working at BJ's on 1/1/2015 (i.e. light blue bar divided by dark blue bar, gray bar divided by black bar).

Thus, for example, the interpretation of the bar when X=17 is as follows. There were about 10,000 employees in control worksites who were employed at BJ’s on 1/1/2014 and who worked through the first 17 weeks of 2014 (dark blue bar). Among these employees, about 79% (or about 7,900) were still working on 1/1/2015 (light blue bar). The same retention of 79% was found among employees in treatment worksites—calculated using the gray (numerator) and black (denominator) bars. The bar originating at X=0 represents the case of no sample restrictions (i.e. all employees in the data).

[figure not shown]

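### The absenteeism models use no pre-program absence value; if the 2014 payroll holds sick and personal hours, adding the worksite's 2014 rate is a cheap gain in precision

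*Combined protocol and SAP*

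**What the plan says.** Section IV.A1 defines absenteeism as sick plus personal hours over sick, personal and worked hours. The source file records each employee's "hours (including working hours, vacation, sick time, personal time) and earnings in each pay period".

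Section VI.A introduces X as a "vector of covariates that may help improve precision as well as account for chance differences in characteristics between treatment and control groups". It lists age, sex, their interactions, race, full-time status, hourly status and job type. The Table 3 notes add Cigna coverage: "All regressions will include demographic and employment controls (age, sex, age-sex interactions, race/ethnicity, Cigna coverage status, full-time status, paid hourly status, and job category". Equation (4), the first stage of the 2SLS model, and equation (3), the second, use the same X. In VI.E the worksite vector "comprises the same set of observable characteristics for individuals, aggregated to the worksite level using weighted averages". The phase 1 specifications in VI.F, equations (7) to (9), add no further covariate, and the balance weights in V.B use only age, sex and race.

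On earlier data, VI.C defines the stable subsample as "employees who had worked continuously for 13 weeks prior to the wellness program", and Appendix 2 says "we take samples of treatment (T) and control (C) workers who were employed for varying numbers of consecutive weeks starting on 1/1/2014". Table 8 Panel D reports some pre-randomization health-insurance and spending values but no absence rate. Table 9 covers demographics only.

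**The concern.** A person's or a worksite's earlier absence rate is the most direct available predictor of its later rate. The plan gives X two jobs, precision and chance imbalance, and leaves out the covariate best suited to both for this outcome.

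Precision matters because inference rests on 20 or 25 treated worksites. Chance imbalance matters because V.B itself reports that the arms differ by race and geography and accepts that unobserved differences may remain. A pre-program gap in absence between the arms would not be seen in the balance tables and would not be adjusted for in the models.

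**Working it through.** The plan states no power, alpha, detectable effect, intracluster correlation (ICC) or baseline correlation for absenteeism, so it has no figure to reproduce. Two-sided 5%, 80% power, rho and the ICC are assumptions here.

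**Inputs**
- Table 3, control group, mean (SD), n: worksites 2.90 (0.35), 135; all employees 2.23 (2.30), 41,376; stably employed 3.39 (1.97), 13,000.
- Treated worksites (VI.E): 20 in the base worksite model, 25 in the alternative.
- Treated employees (Table 8): 7,288 in all, 2,344 stably employed.
- Totals agree with Table 10: 7,288 + 41,376 = 48,664 and 2,344 + 13,000 = 15,344.

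**Worksite level**
- SE = SD × √(1/nT + 1/nC). With 20 treated sites: 0.35 × √(1/20 + 1/135) = 0.0839. With 25: 0.35 × √(1/25 + 1/135) = 0.0762.
- Detectable difference = (1.960 + 0.842) × SE = 0.235 points (8.1% of 2.90) with 20 sites, or 0.213 (7.4%) with 25.
- A baseline covariate multiplies the SE by √(1 − rho²), where rho is the correlation left after the existing X. Power at the unadjusted detectable difference is Φ(2.802/√(1 − rho²) − 1.960).

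| rho | SE reduction | Detectable difference, 20 v 135 | 25 v 135 | Power |
|---|---|---|---|---|
| 0 | none | 0.235 | 0.213 | 80.0% |
| 0.1 | 0.5% | 0.234 | 0.212 | 80.4% |
| 0.2 | 2% | 0.230 | 0.209 | 81.6% |
| 0.3 | 5% | 0.224 | 0.204 | 83.6% |
| 0.5 | 13% | 0.203 | 0.185 | 89.9% |
| 0.7 | 29% | 0.168 | 0.152 | 97.5% |

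These figures use raw SDs and a simple difference in means. They ignore the regression weights and the exposure interaction.

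**Employee level**
- A crude ICC for all employees: 41,376/135 = 306.5 per site; (0.35² − 2.30²/306.5)/2.30² = 0.020. For the stably employed, 13,000/135 = 96.3 per site gives 0.021. I use 0.02.
- SE² = vb(1/25 + 1/135) + vw(1/nT + 1/nC), where vb = ICC × SD² and vw = (1 − ICC) × SD². The worksite rate multiplies vb by (1 − rho²). The individual rate multiplies vw by (1 − share × rho²), where share is the fraction of employees with an own baseline.
- All employees: share = 15,344/48,664 = 31.5%. Unadjusted SE 0.0765, detectable difference 0.214. At rho 0.5 the worksite rate alone cuts the SE by 11.4%, the individual rate alone by 0.6%, and both by 12.0%. For ICC from 0.005 to 0.05 the joint cut is 10% to 13%.
- Stably employed: share = 1. Unadjusted SE 0.0748, detectable difference 0.210. At rho 0.5 the worksite rate alone cuts the SE by 8.6%, the individual rate alone by 4.4%, and both by 13.4%.

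**Length of the individual record.** Appendix 2 counts the 13 weeks back from 3/1/2015. Thirteen weeks are 91 days; January and February 2015 take 59, which leaves 32 days, or about 4.6 weeks, before 1/1/2015. Table 1 puts the program announcement in January 2015, so the later weeks are not a clean baseline. Many employees will have a longer 2014 record, but only this much is guaranteed.

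**The case against.** The strongest reply has four parts.

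- **Availability is inferred.** IV.A speaks of administrative data for the study period, which starts in January 2015. The Appendix 2 counts could come from hire and termination dates alone, and the employment rows of Table 8 Panel D come from the first entry in the treatment period. A reader might infer that 2014 absence records are in hand; the documents make that likely but do not state it. This stands, and the fix is conditional on it.
- **Individual baselines are limited.** A reader might infer that every absenteeism model could use each employee's own prior rate. Under the 13-week definition only 31.5% of the main sample has one, and the guaranteed record is short and therefore noisy. This also stands, and it is why the worksite rate leads the fix.
- **Rho is unknown, and turnover may hold it down.** Clubs average 118 employees at a time but 304 over the study. From Table 3, employees outside the stable subsample supply about 41% of control employment days: 1 − (13,000 × 786.57)/(41,376 × 416.69). A 2014 site rate partly describes a different workforce. This stands.
- **The plan is valid without the covariate.** A reader might infer that the omission biases the intention-to-treat estimate. It does not: assignment was randomized by worksite, and a chance baseline gap is sampling variation that the standard error already reflects.

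None of this is a reason to leave the covariate out if the fields exist. A weak baseline gains little and introduces no bias.

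**Conclusion.** The omission is clear: no absenteeism model, weight or balance table uses a pre-program absence value, although the plan says its covariates serve precision and chance imbalance. The consequence is lost efficiency and an unadjusted chance difference, not bias or an invalid analysis.

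The size depends on a correlation that the documents do not give. Below rho 0.3 the gain is under 5% of the SE, and near 0.1 it is negligible. At 0.5 the worksite-level detectable difference falls from 0.235 to 0.203 points. In the main employee sample nearly all the gain comes from the worksite rate. This is a cheap improvement, conditional on the 2014 payroll extract holding sick and personal hours.

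**What to change.** 1. Ask the sponsor to confirm that the 2014 payroll extract holds sick, personal and worked hours. If it does not, the point lapses.
2. Estimate the baseline-to-follow-up correlation, beyond X, in control worksites only. The plan was already built by examining control-group outcomes, so this needs no comparison of arms.
3. Add the initial worksite's 2014 absence ratio, defined as for the outcome, to X in equation (6) and in all employee-level absenteeism models, including the stably employed models and both 2SLS stages. New hires then have a value too.
4. In the stably employed models also add each employee's own ratio over the available pre-January-2015 pay periods, and state that the guaranteed window is only about 4 to 5 weeks.
5. Add the individual rate to the Table 8 Panel D balance check and the worksite rate to Table 9.
6. Keep the current model as a sensitivity analysis.

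The cost is SAP wording, a derived ratio at two levels, and one degree of freedom for the worksite term among 155 to 160 worksites. A noisy individual covariate limits the gain. The change should be fixed before the arms are compared over the three-year window. The first 18 months have already been analyzed, so the SAP should say when and why the covariate was added.
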